6.11.1. Primary Efficacy Hypothesis, Endpoint, and Analysis

The primary efficacy hypothesis is that 38% Silver Diamine Fluoride (SDF) will arrest cavitated caries lesions (ICDAS 5 or 6) in primary teeth, measured by a change in dentin hardness, without a change in ICDAS severity score, after a single application (measured at 6 months). This occurs as a result of the halting of the caries disease process, which occurs very soon after application of SDF due to its strong antimicrobial and remineralizing properties.

The proportion of arrested cavities at the 6-month visit will be compared between the SDF and placebo-treated groups first using a generalized estimating equation (GEE) model with a logit link for the lesion-specific binary outcome yes/no lesion arrest at the 6-month visit, using an exchangeable correlation to account for non-independence among multiple treated lesions within a participant. The GEE model will include study site as a covariate due to stratified randomization by site.

Trial teeth that cause pain due to caries, pulpal exposure, mobility, signs of pulpal infection (abscess, fistula, swelling) will be exited from the trial and referred for appropriate care (early exit strategy), and will be considered treatment failures (non-arrest) in the analysis of the primary efficacy outcome. Treatment failures from the early exit strategy and timing of the early exit are determined from the subject disposition (withdrawal from the study with reasons related to adverse event or study tooth abscess, pulpal involvement, or pain), lesion withdrawal from the study (reason for lesion withdrawal study tooth abscess, fistula, pulpal involvement, or pain), lesion examination (notes for study tooth abscess, fistula, pulpal involvement, or pain), and adverse events. In short, any lesions removed from the trial due to the “early exit strategy” will be considered treatment failures – non-arrest of the lesion and presence of pain and/or infection – and thus will not be considered to be missing data.

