The use of 38% SDF for caries management is drawing increasing attention throughout the world. Recent systematic reviews and meta-analyses of existing RCT or quasi randomized clinical trials have concluded that 38% SDF is a potentially safe, non-invasive, quick, simple to use, and potentially effective agent, with reported effect sizes for percentages of primary teeth with arrested cavitated caries lesions from 66% (Gao et al., 2016a; Mei et al., 2016) to 81% (Gao et al., 2016b). SDF has been used since the 1970s in Asia as a cavity-arresting and anti-hypersensitivity agent. The literature reports a very high percentage of caries lesion arrest after a single application of SDF (~79%; Zhi et al., 2012), with increases after repeated application after 6 months (~91%; Zhi et al., 2012). This is the reason for assessing the effect of SDF after a single application, and also after being applied twice, approximately 6 months apart. As children will be clinically examined at baseline and 3, 6 and 8 month visits in this trial, and SDF applied at baseline and approximately 6 months post-baseline, we will be able to evaluate the effect after 1 and 2 applications. Regarding application method, no caries removal is necessary prior to application (Chu et al., 2002). Lesions are first cleaned of food debris and gross visible plaque, dried, and then the solution is painted on the dentin of each targeted cavitated lesion using a standardized applicator. One drop (approximately 100 μ l) may treat many lesions, depending on their size. We will use up to 2 drops per child per visit in this trial. The arrest happens very quickly after application: 72% (95% CI: 55-84%) of cavities turned hard within 2 weeks when treated once with SDF vs. 5% (95% CI: 0-16%) when treated with a placebo (i.e., water) in a recent short-term RCT conducted in Head Start programs (Milgrom et al., 2018). Limited data suggests there might be a difference in efficacy based on lesion location and size (Zhi et al., 2012), thus we will use these variables as covariates in our analyses.

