4. SAMPLE SIZE

The population will be children 12-71 months of age at the baseline caries examination attending early childhood education programs or recruited from clinics associated with the Michigan, Iowa or New York clinical trial sites.

The primary outcome of this trial is the proportion of arrested caries lesions approximately 6 months from the baseline visit (i.e., lesions that have changed from soft to hard over the trial period according to the ICDAS II activity criteria). A 10% difference in the proportion of arrested caries lesions between the SDF and placebo groups will be considered clinically significant. Prior studies in the literature of SDF using this outcome in primary cavitated lesions have shown a wide range for the proportion of arrested caries lesions for both SDF-treated and placebo-treated or untreated lesions; therefore the 10% difference in proportions was calculated assuming 55% versus 45% arrested caries lesions for SDF compared to placebo. In prior studies, an average of 4 lesions was treated per participant, with a within-participant correlation of 0.5; we are conservatively assuming 3 lesions per participant. The sample size calculations used a 2-sided test for a difference in proportions with cluster randomization (participant as the cluster) at significance level $\alpha=0.1\%$, with 80% power to detect a superiority difference of 10% for SDF compared to placebo. The calculations also account for the use of an early stopping rule for efficacy and futility. The interim analysis will be performed after approximately half of the sample has completed the 6-month examinations. A Lan-Demets spending function with an O'Brien-Fleming type boundary will be used, with p-values for efficacy at 0.000001709 and 0.00099938 at 50% and 100% completion, respectively. Non-binding p-values for stopping due to futility at 50% and 100% completion will be 0.2336928 and 0.00099938, respectively. With the above assumptions, the trial will require 1144 participants to be enrolled. Sample size calculations were made using East version 6.

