6.1. Statistical Comparisons

All statistical comparisons will be made using a two-sided test. The interim and final analyses will be conducted using p-value thresholds of 0.000001709 and 0.00099938, respectively, for the primary analysis. The overall type I error for interim and final primary endpoint analysis is two-sided $\alpha=0.1\%$.

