6.11.5. Tertiary Efficacy Hypotheses, Endpoints, and Analyses

The P-CPQ (Sub-Aim 4a), FIS (Sub-Aim 4a), and satisfaction and acceptability scores (Sub-Aim 4b) will be compared between the SDF and placebo-treated groups using analysis of covariance (ANCOVA). The models will include study site as a covariate due to stratified randomization by site. Additional ANCOVA models will consider the effects of covariates and their interactions with the treatment effect.

Changes in the color of treated lesions over time will be summarized by group.

The family's experiences with ECC, child's brushing and dietary habits, and color change will be examined as additional covariates for the analyses of satisfaction and acceptability scores.

The total number of episodes of pain associated with trial teeth per participant (calculated by adding all reports of pain throughout the trial verified by a clinical exam to be associated with a trial tooth) during the follow-up period and the DDQ scores will be summarized for the SDF and placebo treated groups. Due to the small number of participants with any pain, no statistical comparisons will be performed for the number of episodes of pain or the DDQ scores.

Additional analyses of the proportion of arrested lesions at 3-months, 6-months, and 8-months will extend the GEE models for binary outcomes to include covariates and their interactions with the treatment effect; covariates will include race/ethnicity, gender, age, trial site, initial ICDAS score, tooth location (anterior/posterior; as there are some data in the literature to suggest a difference in SDF efficacy) and number of affected teeth. Interactions of the covariates with treatment will be explored to examine the results for differential treatment effects. However, the analyses are not specifically powered to detect these interactions. Due to the small number of participants with any pain, no analyses which include covariate effects on the binary pain outcomes will be performed.

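### Adding baseline ICDAS score, tooth location and age to the site-only primary GEE would be a cheap efficiency gain; the site-only model is itself valid

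*SAP*

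**What the plan says.** SAP 6.11.1 compares lesion arrest at 6 months with a logit-link GEE, exchangeable within child. On covariates it says: "The GEE model will include study site as a covariate due to stratified randomization by site". Protocol 12.4 (Aim 1) specifies the same site-only model. Randomisation is stratified by site alone (Protocol 5.4, SAP 5) and takes place after the baseline ICDAS examination (Protocol 7.2, SAP 5).

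The baseline lesion variables and age appear elsewhere:

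- Protocol 2.2 reports limited evidence that efficacy might vary with lesion location and size, and continues "thus we will use these variables as covariates in our analyses".
- Protocol 12.4 puts them in secondary analyses. SAP 6.11.5 puts them in additional GEE models at 3, 6 and 8 months: "covariates will include race/ethnicity, gender, age, trial site, initial ICDAS score, tooth location" and number of affected teeth, with treatment interactions.
- SAP 6.11 uses age, initial ICDAS score and tooth location, among others, to impute missing lesion arrest.

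SAP 6.11 also mentions collapsing categories of covariates for the GEE model without saying which GEE model is meant. SAP 6.11.2 defines the population summary as an odds ratio and adds a population risk difference with a 95% interval. Neither document says how the risk difference will be obtained from a logit GEE.

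**The concern.** The plan uses three baseline variables to predict the outcome where it is missing, then leaves them out of the model that estimates the treatment effect. If they predict arrest, adjusting for them removes outcome variation unrelated to treatment and corrects for chance imbalance in lesion mix, which site stratification does not control. The primary test is at an overall two-sided 0.1%, "with 80% power to detect a superiority difference of 10% for SDF compared to placebo". Any precision already available in the data is therefore worth having if the effect is near the planning value.

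**Working it through.** **Step 1. Reproduce the planned size.** Inputs from SAP 4: "assuming 55% versus 45% arrested caries lesions for SDF compared to placebo"; "within-participant correlation of 0.5; we are conservatively assuming 3 lesions per participant"; two-sided alpha 0.001; power 80%.

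- Lesions per arm if independent (pooled null variance): (3.2905 × √0.5 + 0.8416 × √0.495)² / 0.10² = 852.
- Design effect: 1 + (3 − 1) × 0.5 = 2.
- Children: 852 × 2 / 3 × 2 arms = 1136. With unpooled variance, 1127.
- With the interim efficacy and futility boundaries: 1142 (unpooled) or 1154 (pooled).

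The stated 1144 is reproduced, with no covariate adjustment in it.

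**Step 2. State what must be assumed.** The documents give no prognostic strength for ICDAS score, location or age. The assumed lesion-level odds ratios were 1, 1.5, 2 or 3 for ICDAS 6 versus 5 and for posterior versus anterior, with 1, 1.1, 1.2 or 1.3 per year of age. About 31% of lesions were ICDAS 6 and half were posterior, both partly clustered within child. Age was constant within child.

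**Step 3. Simulate the planned design.** There were 1144 children with 3 lesions each, three sites, marginal arrest of 45% and 55%, within-child correlation 0.5 and no missing data. Each setting had 1,500 trials, tested once at the final threshold of 0.00099938. Both models were fitted to the same simulated trials.

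| Assumed OR (ICDAS, location / age) | Outcome variance explained | Power, site-only | Power, adjusted | Change (points) | Variance ratio of standardised risk difference | N matching 1144 unadjusted |
|---|---|---|---|---|---|---|
| 1 / 1 | 0% | 80.0% | 80.0% | 0 | 1.001 | 1144 |
| 1.5 / 1.1 | 2.3% | 79.1% | 80.5% | 1.4 | 0.968 | 1117 |
| 2 / 1.2 | 6.5% | 81.3% | 85.1% | 3.8 | 0.933 | 1076 |
| 3 / 1.3 | 13.7% | 79.7% | 87.2% | 7.5 | 0.843 | 994 |

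The last column is 1144 × (mean Z site-only / mean Z adjusted)²; in the strongest setting, 1144 × (4.118 / 4.417)² = 994. Monte Carlo error is about 1 point for each power figure.

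**Step 4. Check the variance ratios by hand.** With 3 lesions and correlation 0.5, the variance of a child's mean is two thirds of the lesion variance. Covariates explaining a share R² of lesion variance remove about R²/2 of it if they vary independently within child, and about 1.5R² if they are constant within child. For R² = 0.137 that is 7% to 21%; the simulation gives 16%. For R² = 0.065 it is 3% to 10%; the simulation gives 7%. The gain therefore depends on how the covariates cluster as well as on their strength.

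**Step 5. See where the gain appears.** It is not a smaller standard error for the log odds ratio. In the strongest setting that standard error rises from 0.097 to 0.105, while the log odds ratio moves from 0.400 to 0.464 because the adjusted coefficient is conditional on more variables. The gain in precision shows in the standardised risk difference, whose standard deviation falls from 0.0247 to 0.0227.

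**The case against.** A reader might infer that the protocol says lesion size and location affect efficacy, promised them as covariates in the primary model, and that the SAP dropped them. The documents do not support this. Protocol 2.2 is tentative, speaks of analyses in general, and does not mention age. Both documents meet the commitment through the covariate models in Protocol 12.4 and SAP 6.11.5. A difference in efficacy is also effect modification, which is not evidence of the prognostic strength that yields precision.

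It is equally tempting to call the gain free. It is not quite. The model coefficient becomes a more conditional odds ratio, so the summary in SAP 6.11.2 would need a standardisation step, repeated within imputation. If the variables are not prognostic, nothing is gained.

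Timing is the strongest practical objection. SAP 9 records requests from a pre-NDA meeting and populations of interim participants, and SAP 6.11.5 already refers to few participants having pain. This suggests that some data had been seen. It does not show that treatment-level results were known to those writing the plan: SAP 5 keeps the project biostatistician masked until after database lock, and SAP 7 describes firewalls around interim results. If they were known, changing the primary model would not be pre-specified.

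The need may also be small. Protocol 2.2 cites a short-term trial with 72% versus 5% arrest; at an effect that large, power is essentially 100% under either model.

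All of this stands as a limit on the point. None of it shows that adjustment would do harm if settled in time.

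**Conclusion.** This is an efficiency improvement and not an error. The site-only analysis is randomised, adjusts for its only stratification factor, allows for within-child correlation and follows the protocol. No bias or type I error problem is shown.

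Adjustment cost no power in any setting tested. The gain ranges from 0 to 7.5 power points and from no reduction to about 16% in the variance of the risk difference, depending wholly on assumed prognostic strength and clustering. The figures also assume complete data and a true difference of 10 points. At much larger effects the choice makes no practical difference to power.

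**What to change.** If treatment-level data have not been seen:

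- Add initial ICDAS score, anterior/posterior location and age as main effects, alongside site, to the GEE in SAP 6.11.1.
- Report the standardised (marginal) risk difference and odds ratio with robust or bootstrap standard errors, so that the SAP 6.11.2 summary is kept. State which statistic carries the primary test.
- Use the same model at the interim and final looks and in the tipping-point analysis.
- Keep the site-only model as a sensitivity analysis.

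If data have been unmasked, keep site-only as primary and add the main-effects model as a named supportive analysis.

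In either case, state how the risk difference and its interval are computed, and say which GEE model the collapsed covariates in SAP 6.11 belong to.

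The cost is SAP wording and programming: the marginal effect and its standard error must be derived in each of the 25 imputed datasets before pooling. No extra data or participants are needed.

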6.11.2. Primary Outcome Estimand

Estimand attributes for the primary efficacy analysis are defined according to the following attributes specified in ICH E9(R1) Addendum:

- **Treatment** – 38% percent Silver Diamine Fluoride (SDF) applied once at baseline.
- **Population** – Children between 12-71 months of age at baseline, up to the day the child turns 6 years old with S-ECC [*defined as: In children younger than age 3, any sign (non-cavitated or cavitated lesion) of caries in any tooth surface (i.e., most common for this age group will be on erupted smooth surfaces). From ages 3 through 5, ≥ 1 dmfs in maxillary anterior teeth; or a dmfs score of ≥ 4 (age 3), ≥ 5 (age 4), or ≥ 6 (age 5) constitutes S-ECC. Note: The “d” component of the dmfs index is defined as including cavitated and non-cavitated lesions, thus ICDAS>1] and with at least one SDF-target tooth with soft cavitated caries lesions extending into dentin [ICDAS 5 or 6 (Protocol Appendix A)]; and/or cavitated lesion(s) that allow for direct hardness assessment and application of SDF (microbrush applicator must fit the cavity and be able to access all exposed dentin).*
- **Primary Variable** – Number of arrested cavities at the 6-month visit.

- **Population level summary** – Odds Ratio comparing odds of arrested cavities in the treated group vs odds in the placebo group at month 6 visit. Population risk difference at month 6 along with its 95% confidence intervals will also be presented.
- **Intercurrent event (IE)** – Study discontinuation before 6 months visit due to pain (early exit).
- **Strategy** – The following strategy will be used to account for IEs - any efficacy data collected after the occurrence of the intercurrent event (early exit due to pain before visit at month 6) will be set to failure i.e. any lesions removed from the trial due to the “early exit strategy” will be considered treatment failures – non-arrest of the lesion and presence of pain and/or infection – and thus will not be considered to be missing data.

6.11.3. Primary Efficacy Endpoint: Sensitivity Analyses

Tipping Point Analyses:

A sensitivity / tipping point analysis will also be performed to evaluate the MAR assumption for the missing primary efficacy outcome (caries arrest at 6 months). A pattern-mixture approach to the missing data imputation (missing not at random, MNAR) will be applied to the logistic regression model used for imputing the missing caries arrest at 6 months outcome from the variables described above. To represent MNAR, a range of shift parameters will be used to adjust the log odds ratios for the SDF-treated group. The tipping point will be identified as the amount of shift needed to change the statistical significance of the treatment comparison using the primary efficacy analysis. The size of the shift required to change the statistical significance will be used to gauge the plausibility of the MAR assumption.

Additional Sensitivity Analysis (Visit Windows):

Due to the COVID-19 pandemic and associated illnesses, precautions, and shutdowns, some study subjects were unable to be seen for in-person visits within the study windows. The primary analysis will be repeated using wider windows after the 6-month visit, 7-month intermediate contact, and 8- month visit as follows:

- additional 10 days prior to the original window opening for all visits and intermediate contacts
- additional 10 days after the original window closure for all intermediate contacts
- 6-month visit occurred within the standard window
 - use standard windows for the 7-month contact and 8-month visit
- 6-month visit window expanded to include days +202 through +242 post-baseline in addition to the standard window
 - if the 6-month visit occurred within the expanded window, the 7-month window used 20- 40 days from the 6-month visit, and the 8-month window used 41-79 days from the 6- month visit,
 - if the 6-month visit was completed but was more than 242 days post-baseline, the 7- month window used 20-40 days from the 6-month visit, and the 8-month window used 41-79 days from the 6-month visit
- 6-month visit missed
 - 7-month window 200-270 days post-baseline, 8-month window 221-300 days post-baseline

The wider window for the 6-month visit still falls within a reasonable range for a 6-month recall visit in a clinical setting. Data collected outside the allowable visit or contact windows will be treated as missing data as described above in [Section 6.11.1](#).

6.11.4. Secondary Efficacy Hypotheses, Endpoints, and Analyses

The gatekeeping procedure will assess the hypotheses associated with the two key secondary endpoints in the following prescribed hierarchy. Each endpoint will be assessed using a two-sided $\alpha=0.1\%$ significance level, however the second endpoint in the hierarchy below will be gated by the first endpoint meeting significance. Otherwise, no inference will be drawn on the second endpoint in the hierarchy below, however results with p-values will still be calculated and presented in the table outputs.

1. Secondary Endpoint #1: Cavitated Caries Lesion Arrest at 8 months (Aim 2)

This secondary endpoint will be tested first. The same GEE model for binary outcomes as used for Aim 1 will be used to compare the proportion of arrested lesions at 8-months to examine Aim 2.

2. Secondary Endpoint #2: Pain (Aim 3)

This secondary endpoint will be tested second only if the first secondary endpoint reaches statistical significance.

Aim 3: At the 8-month visits, the proportion of treated lesions that have experienced pain during the follow-up period before or at the visit will be compared between the SDF and placebo-treated groups using GEE models with a logit link for the lesion-specific binary outcomes yes/no lesion pain at each visit, using an exchangeable correlation to account for non- independence among multiple treated lesions within a participant. The GEE models will include study site as a covariate due to stratified randomization by site.

Other Sub-Aim Secondary Endpoint Analyses:

For Sub-Aim 2a (Cavitated caries lesion arrest at 3 months), the same GEE model for binary outcomes as used for Aim 1 will be used to compare the proportion of arrested lesions at 3 months to examine Aim 2a. Sub-Aim 2a is not included in the hierarchical testing strategy.

For Sub-Aim 2b (Stability of the effect of one application of 38% SDF on caries lesion arrest between 3 and 6 months), a longitudinal (repeated measures) model for binary data that incorporates both the correlation within each subject at each time and across the time points will be used to compare the proportion of arrested caries lesions at 3 and 6 months. Study site will be included as a covariate due to stratified randomization by site.

For Sub-Aim 3a (Pain at 3 and 6 months): At the 3-, 6-month visits, the proportion of treated lesions that have experienced pain during the follow-up period before or at the visit will be compared between the SDF and placebo-treated groups using GEE models with a logit link for the lesion-specific binary outcomes yes/no lesion pain at each visit, using an exchangeable correlation to account for non- independence among multiple treated lesions within a participant. The GEE models will include study site as a covariate due to stratified randomization by site.

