6.11. Efficacy Analyses

All efficacy endpoints will be analyzed using the ITT and ITT2 populations. Additional analyses will be performed on the PP and PP2 populations.

The null hypothesis is no difference between the treatment groups and the alternative hypothesis is there is a difference between treatment groups. All statistical comparisons will be made using a two-sided test. The interim and final analyses will be conducted using p-value thresholds of 0.000001709 and 0.00099938, respectively. The overall type I error for interim and final primary endpoint analysis is two-sided $\alpha=0.1\%$.

Several categorical variables that are to be used as covariates in the GEE model will have categories collapsed due to small sample sizes. Race and ethnicity will be combined to form a single combined variable defined as: Hispanic or Latino if a subject indicated as such for ethnicity, multiracial if more than one race was selected, Black, White, “Asian or ‘American Indian or Alaska Native’ or ‘Native Hawaiian / Other Pacific Islander’”, “Not Reported” or Unknown”. Within the ‘tooth’ variable, lower incisors (LL1, LL2, LR1, LR2) will be combined into a single category and LR6 will be combined with LR5 for the imputation models for the lesion arrest outcomes, and combined into upper jaw / lower jaw and anterior teeth (upper and lower central incisors, lateral incisors, and canines) / posterior teeth (upper and lower molars on the) variables for the imputation models for the presence of tooth pain outcomes. For the imputation models for the presence of tooth pain outcomes, child ages 1 and 2 years will be combined.

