8. INTERIM ANALYSIS

A formal interim analysis of the primary endpoint will be conducted after approximately half of the sample has completed the 6-month examination. A Lan-Demets spending function with an O'Brien-Fleming type boundary will be used, with p-values for efficacy at 0.000001709 and 0.00099938 at 50% and 100% completion, respectively. Non-binding p-values for stopping due to futility at 50% and 100% completion will be 0.2336928 and 0.00099938, respectively.

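### SAP 6.11.4 does not make the key secondary hierarchy conditional on the primary endpoint or name the population that decides it, so family-wise error over primary and key secondaries is not controlled

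*SAP*

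**What the plan says.** SAP 6.11.4 describes a gatekeeping procedure for two key secondary endpoints: lesion arrest at 8 months (Aim 2), then pain (Aim 3). Each has a two-sided 0.1% level; "however the second endpoint in the hierarchy below will be gated by the first endpoint meeting significance". The first secondary is simply tested first. Neither 6.11.4, nor SAP 3.2 where the key secondaries are identified, nor 6.1, 6.11 or 8 conditions it on the primary.

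On populations, SAP 6.11 says: "All efficacy endpoints will be analyzed using the ITT and ITT2 populations". ITT2 is the set of randomised participants included in the interim analysis (SAP 6.2.4), a subset of ITT.

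On thresholds, SAP 6.1 says: "The interim and final analyses will be conducted using p-value thresholds of 0.000001709 and 0.00099938, respectively, for the primary analysis". SAP 6.11 repeats the two figures under the general efficacy heading without limiting them to the primary. SAP 8 confines the formal interim to the primary: "A formal interim analysis of the primary endpoint will be conducted after approximately half of the sample has completed the 6-month examination".

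The only overall error statement concerns the primary: "The overall type I error for interim and final primary endpoint analysis is two-sided" 0.1% (SAP 6.1, repeated in 6.11).

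**The concern.** A hierarchy that withholds inference on the second secondary when the first fails exists to control error. It controls error across the trial's main claims only if it starts from the primary. Here it starts one step later, so the primary and 8-month arrest each carry 0.1% in parallel. Followed as written, the plan allows a positive key secondary claim from a trial that missed its primary endpoint.

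The second gap is the decision rule for the secondaries. Two nested populations are analysed, and both ITT and ITT2 are described as being for efficacy analyses, whereas PP and PP2 are called supportive. Three sections leave the threshold unclear: 6.1 ties the split thresholds to the primary, 6.11 does not, and 6.11.4 gives a flat 0.1%. For 8-month arrest in ITT2 a reader could apply 0.000001709 or 0.001, a ratio of 0.001 / 0.000001709 ≈ 585.

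**Working it through.** **Inputs from the documents.** Two-sided tests and overall alpha of 0.001 for the primary (SAP 6.1); efficacy thresholds 0.000001709 at 50% and 0.00099938 at 100%, Lan-DeMets with an O'Brien-Fleming type boundary (SAP 8); 0.001 two-sided for each key secondary (SAP 6.11.4).

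**Assumptions.** The documents give no correlation between the 6-month and 8-month arrest test statistics; I use 0 to 0.8. They give no 8-month information fraction for ITT2; I use 50%, then 70% to 90%. All figures below are under the global null.

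**Step 1: reproduce the primary's 0.1%.** Spending in each 0.0005 tail at t = 0.5 is 2[1 − Φ(z₀.₀₀₀₂₅ / √0.5)], with z₀.₀₀₀₂₅ = 3.4808, so 3.4808 / 0.7071 = 4.9225. Over both tails this gives 0.0000017086 (stated 0.000001709). Solving for the final boundary with corr(Z₁, Z₂) = √0.5 gives a nominal p of 0.00099936 (stated 0.00099938). Putting the stated thresholds back in (|Z₁| > 4.7851 or |Z₂| > 3.2907) gives an overall two-sided error of 0.00100. The claim for the primary holds.

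**Step 2: primary plus one ungated test of 8-month arrest.** Each endpoint is tested at 0.001 (critical value 3.2905), and P(either rejects) is taken from the bivariate normal. In the independent case this is 1 − (1 − 0.001)² = 0.001999.

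| Assumed correlation | P(at least one false positive) |
|---|---|
| 0 | 0.200% |
| 0.5 | 0.196% |
| 0.8 | 0.176% |

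Giving the primary its group-sequential boundaries instead makes no material difference: simulation with 40 million draws per correlation gave 0.200%, 0.196% and 0.177%.

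**Step 3: if ITT2 and ITT both counted for 8-month arrest at 0.1%.** P(|Z₁| > 3.2905 or |Z₂| > 3.2905), with corr(Z₁, Z₂) = √t:

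| Assumed information in ITT2 (t) | Error for 8-month arrest alone |
|---|---|
| 50% | 0.186% |
| 70% | 0.171% |
| 80% | 0.160% |
| 90% | 0.144% |

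Adding the primary on its stated boundaries, with t = 0.5, simulation gave 0.285%, 0.280% and 0.260% at correlations 0, 0.5 and 0.8. The independent case checks directly: 1 − (1 − 0.00100)(1 − 0.001857) = 0.00286.

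**Step 4: with a primary gate and one deciding test.** If the primary null is true, a false positive on any endpoint requires the primary to reject, which has probability at most 0.1%. If the primary effect is real but the 8-month null is true, a false positive requires the single 0.1% test of 8-month arrest to reject. The same argument applies to pain. Family-wise error is therefore at most 0.10%.

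**The case against.** The strongest reply is that the plan never promises what it is said to lack. Its 0.1% statement covers only the primary, and Step 1 confirms it. A reader might infer that the missing gate breaks the stated 0.1% control; it does not, because the primary's error does not depend on how the secondaries are tested. This part of the reply stands in full.

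A reader might also infer that every endpoint receives two full 0.1% looks. The documents do not support that. The primary has the split thresholds. For the secondaries, 6.11 says that endpoints are analysed in both populations, not that either result is enough for a claim. The formal interim covers the primary only, and SAP 9 records ITT2 as added at the FDA's request from the pre-NDA meeting, so it may be a reporting population. The unrestricted thresholds in 6.11 could even be read as applying to the secondaries. This also stands: the double look is a possible reading of an unclear text.

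Finally, Protocol 3.1 and 3.2.2 say that the secondary outcomes are not meant to support labelling claims, and the absolute error stays below 0.3% on any reading considered here. That limits the consequence but does not remove the point. The SAP does not repeat the labelling caveat in its own aims and outcomes, although its list of changes does not withdraw it, and it adds a formal testing strategy for key secondaries (SAP 9). A strategy of that kind should state where it begins.

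**Conclusion.** The point holds as a gap in family-wise control, not as a failure of the primary's alpha. With 8-month arrest tested once, the chance of a false positive across the primary and that endpoint is up to 0.20% (0.176% to 0.200% over assumed correlations of 0.8 to 0). This follows directly from the missing gate.

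The lack of a named deciding population, and the conflict between 6.11 and 6.11.4, are ambiguities to reconcile. Only if both populations were used for inference at 0.1% would 8-month arrest alone reach 0.186% (assuming 50% information; less if ITT2 holds more) and the pair 0.26% to 0.29%. It would be wrong to say that the key secondary itself is tested at two to three times its stated rate: even on that reading it is about 1.86 times, and with one test it is exactly 0.1%.

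**What to change.** In SAP 6.11.4:

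1. State that 8-month arrest is tested only if the primary crosses its efficacy boundary, and pain only if 8-month arrest is then significant.
2. Name one population and one analysis that decide the key secondaries, tested once at two-sided 0.1%, and label the other population's results descriptive. If both looks are meant to count, pre-specify a spending function with a total of 0.1% for the secondaries.
3. Reconcile 6.11 with 6.11.4, either by limiting the split thresholds in 6.11 to the primary, as 6.1 does, or by stating which thresholds the secondaries use.

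The drafting cost is a few sentences, with no change to sample size or data collection. There are two costs in inference. No key secondary claim is possible if the primary fails. If a spending function is chosen and the decision falls at the interim, the secondary threshold there becomes much stricter: 0.000001709 under the stated boundaries. That would weigh most on pain, since SAP 6.11.5 already notes that few participants had any. A single test at 0.1% in one named population avoids that second cost.
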